## Appendix 2. Programming Specifications

- 1) If the age from the Day 1 eCRF is not available, age will be calculated as follows:

Only year is provided for the date of birth (DOB). Use July 1 for the month and day.

- AGE (years) is calculated from the number of days between the DOB and Study Day 1,
- Use the SAS INTCK function to determine the number of “1st-of-month days” (eg, January 1st, February 1st, March 1st) between DOB and Day 1 (inclusive),
- Divide the result in (b) by 12,

AGE = the integer of the result in (c),

Age for laboratory test reference range will be based on the age at the sample collection date.

- 2) All screened participants refer to all participants who are screened (ie, with non-missing screening date) and have a screening number. For summaries the same participant is counted only once.
- 3) Screen failure participants are the participants who were screened and answered “No” for any inclusion criteria or “Yes” for any exclusion criteria regardless of which version of protocol the participant was consented to.
- 4) Participants in the randomized analysis set are defined as participants randomized into the study. IXRSRND is the source to determine whether the subject is randomized (ie, participant with non-missing RGMNDTN in the IXRSRND dataset), and confirmed by the eCRF ENROLL dataset (ie, ENROLLYN = “Yes” in ENROLL dataset).
- 5) Randomized treatment (ie, TRT01P in ADSL) is derived from IXRSRND, while actual treatment received (ie, TRT01A in ADSL) is assigned as the randomized treatment if participant took at least 1 dose of study drug and assigned as blank if the participant was never dosed.
- 6) In the disposition table, the reasons for premature discontinuation are displayed in the order as they appear on the eCRF.
- 7) Body mass index (BMI)

BMI will be calculated only at baseline as follows:

$$\text{— BMI} = (\text{weight [kg]}) / (\text{height [meters]}^2)$$

Baseline height and weight will be used for this calculation if available.

- 8) For demographics tables, “Not Permitted” will be excluded from percentage for detailed race categories summary (i.e. race categories collected on eCRF). For combined Race Category (e.g. Asian, White, Black, Other), “Not Permitted” is included in “Other” and “Other” will be included in the count of percentage.
- 9) TEAE

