#### **8.3.1.2. Safety**

The primary analysis set for safety analyses is defined as the Safety Analysis Set, which will include all participants who (1) are randomized into the study and (2) have received at least 1 dose of study treatment. Participants will be grouped according to the treatment to which they received.

CCI

[REDACTED]

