### **3.1.4. Safety Analysis Set**

The primary analysis set for safety analyses is defined as the Safety Analysis Set, which will include all participants who (1) are randomized into the study and (2) have received at least 1 dose of study treatment. Participants will be grouped according to the treatment which they received.

CCI [REDACTED]

[REDACTED]

[REDACTED]

CCI [REDACTED]

[REDACTED]

[REDACTED]

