## **3.2. Subject Grouping**

For analyses based on the All Randomized Analysis Set, FAS, mFAS or Virology Analysis Set, participants will be grouped according to the treatment to which they were randomized. For the safety analysis set, the actual treatment received will differ from the randomized treatment only when their actual treatment differs from randomized treatment for the entire treatment duration.

CCI [REDACTED]

[REDACTED]

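### SAP Appendix 2 item 5 omits the Section 3.2 exception, so a participant given the wrong treatment throughout would be analysed for safety under the randomized arm

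*SAP*

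**What the plan says.** Three places state an as-treated grouping for safety.

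- Protocol 8.3.1.2: "Participants will be grouped according to the treatment to which they received". Protocol 8.6 repeats the principle for the safety summaries.
- SAP 3.1.4: "Participants will be grouped according to the treatment which they received".
- SAP 3.2 gives the operating rule for the safety set: "the actual treatment received will differ from the randomized treatment only when their actual treatment differs from randomized treatment for the entire treatment duration".

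The programming specification says something different. In SAP Appendix 2 item 5, "Randomized treatment (ie, TRT01P in ADSL) is derived from IXRSRND". Actual treatment (TRT01A) "is assigned as the randomized treatment if participant took at least 1 dose of study drug" and is "assigned as blank if the participant was never dosed". Item 5 gives no exception and does not refer back to Section 3.2.

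SAP 7.6 declares that the safety analyses do not depart from the protocol.

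**The concern.** Under item 5, dosing data decide only whether TRT01A is filled in, never which product it names. For every dosed participant TRT01A therefore equals TRT01P, and the reassignment foreseen in Section 3.2 cannot happen.

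The variable decides the arm in which safety events are counted. The TEAE proportion is the primary safety endpoint (SAP 7.1.6), and the adverse event and laboratory summaries use the Safety Analysis Set (SAP 7.1.7 and 7.2). Suppose a participant randomized to placebo received remdesivir at every infusion, or the reverse. That participant's events, including any serious drug-related event, would appear in the wrong column of a table described as grouped by treatment received. Placebo matches the active product in appearance (protocol 5.2.1) and is dispensed blinded (protocol 5.1.2), so such an error would not be obvious at the bedside. Because SAP 7.6 declares no deviation, a reader of the report would have no reason to suspect it.

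**Working it through.** The plan gives no figure to reproduce here. The check is a comparison of two rules, followed by a bound on the effect.

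**Step 1: apply both rules to the possible dosing patterns**

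| Randomized to | Doses actually given | TRT01A by item 5 | TRT01A by Section 3.2 | Agree? |
|---|---|---|---|---|
| RDV | RDV, RDV, RDV | RDV | RDV | Yes |
| RDV | placebo, RDV, RDV | RDV | RDV | Yes |
| RDV | placebo, placebo, placebo | RDV | placebo | No |
| RDV | placebo once, then stopped | RDV | placebo | No |
| Placebo | RDV, RDV, RDV | placebo | RDV | No |
| Placebo | none | blank | blank | Yes |

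The rules part only when every dose given was the other product. The fourth row reads a course cut short after one wrong dose as a whole course.

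**Step 2: set membership**

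SAP 3.1.4 requires only randomization and at least one dose. TRT01A plays no part in that, so the same participants are in the set under either rule. Only the arm label can change.

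**Step 3: bound on the effect**

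Inputs: 584 randomized (SAP 2.1.1), ratio 1:1 (SAP 1.2). Assumption: all were dosed and split evenly, so n = 584/2 = 292 per arm. If fewer were dosed, the figures below rise slightly.

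Let x of the n participants in an arm have a TEAE, with p = x/n. When a participant with a TEAE is moved out, numerator and denominator both change:

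x/n − (x − 1)/(n − 1) = (1 − p)/(n − 1)

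The arm that receives the participant, with its own p, rises by (1 − p)/(n + 1). Both are at most about 1/292 = 0.34 percentage points, reached as p approaches 0. Moving a participant without a TEAE changes an arm by p/(n − 1) or p/(n + 1), with the same ceiling as p approaches 1.

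The documents give no TEAE rate. Over an assumed range of 20% to 60%, for a moved participant with a TEAE:

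- p = 20%: per-arm change about 0.80/292 = 0.27 points. If both arms have this rate, the difference changes by about 2 × 0.80/292 = 0.55 points.
- p = 60%: per-arm change about 0.40/292 = 0.14 points, and the difference changes by about 2 × 0.40/292 = 0.27 points.

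In a two-way swap (one participant each way, one with a TEAE and one without) the denominators stay fixed. Each arm moves by exactly 1/292, and the difference by 2/292 = 0.68, or about 0.7 points. A swap in which both or neither had a TEAE changes nothing.

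**Step 4: share of an arm affected**

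For k wholly misdosed participants the share is k/292: 0% for k = 0, 0.34% for 1, 0.68% for 2, 1.71% for 5 and 3.42% for 10. The documents do not give k.

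**The case against.** The best defence is that item 5 states the default and Section 3.2 of the same SAP supplies the exception, so a careful programmer would read them together. Nothing in the SAP says that the appendix overrides the body. That is fair, but nothing says the reverse either. Item 5 names the analysis variable and gives a complete rule for both the dosed and the undosed. Code checked against it would pass and still break Section 3.2.

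The consequences are also limited, and these points stand:

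- The TEAE proportion is descriptive; SAP 7.1.6 plans no statistical comparison, so no p-value for that endpoint depends on TRT01A.
- By-subject listings use the randomized group by design (SAP Section 3).
- A whole-course error could surface elsewhere: medication errors are reportable as special situations (protocol 7.7), and important protocol deviations are summarized and listed (SAP 4.3). These routes make a case visible but do not correct its arm in the safety tables.

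A reader might infer that the as-treated safety set can never be produced, or that the safety tables are wrong. The documents support neither. Membership of the set does not depend on item 5. If nobody was misdosed throughout, item 5 yields exactly the grouping promised. If somebody was, the grouping can be obtained once item 5 is corrected and the product given is traced. Nothing in the documents suggests that such an error occurred.

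**Conclusion.** Item 5 contradicts SAP 3.1.4 and 3.2 and protocol 8.3.1.2 and 8.6, and no other section repairs it. It is a stated rule that gives the wrong arm in one defined situation: the other treatment received for the entire course. Outside that situation it does no harm.

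The effect is zero if there were no such cases. Otherwise it is at most about 0.34 points on one arm's TEAE proportion per affected participant, and at most about 0.7 points on the between-arm difference for a two-way swap. Both are ceilings and rest on the assumption of about 292 dosed per arm. For a rare or serious event, the arm in which a single case is counted may matter more than these percentages suggest, but that remains hypothetical. The point is worth correcting because it touches the primary safety endpoint and costs little, not because it is likely to change the safety conclusions.

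**What to change.** Rewrite Appendix 2 item 5 so that TRT01A is:

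- the treatment actually received, when it differs from the randomized treatment for the entire treatment duration, as in Section 3.2;
- otherwise the randomized treatment;
- blank if the participant was never dosed.

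Name the sources used to find such cases: dispensing or vial accountability records, and medication-error or protocol-deviation reports. If the check finds none, say so in the study report, so that the reader knows the as-treated and as-randomized groupings coincide.

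The rule should be settled before the blind is broken. Matching vial numbers to product needs the treatment codes, so before then that step belongs with personnel who are already unblinded; protocol 5.1.2 names an unblinded inventory role.

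The text change is one sentence. The remaining cost is reconciliation. Protocol 5.5 places vial numbers by participant in site accountability records, and the documents do not say that they are in the clinical database. SAP 3.8.1 uses the study drug administration form only for dose dates, so that form may not identify which product was given.

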#### **Events with Missing Onset Day and/or Month**

An event is considered treatment emergent if all of the following 3 criteria are met:

- i. The month and year (or year) of onset date is the same as or after the month and year (or year) of the first dose of study drug, and
- ii. The month and year (or year) of the onset date is the same as or before the month and year (or year) of the 30th day after the date of the last dose of study drug, and
- iii. End date is as follows:

The (complete) end date is on or after the first dose date, or

The month and year (or year) of end date is the same or after the month and year (or year) of the first dose of study drug, or

End date is completely missing

#### **Events with Completely Missing Onset Date**

An AE with a completely missing onset date is defined as TEAE if end date meets any of the 3 criteria specified above.

- 10) The precision in reporting numerical values should be as follows:

Raw measurements will be reported the same as the data captured electronically or on the eCRF for all but hematology and chemistry values.

Standard deviation and standard error will be reported to one more significant decimal place than the raw measurement.

Mean, median, minimum, Q1, Q3, and maximum will be reported to the same number of decimal places of the raw measurements.

Exceptions may be considered; for example, if more than 4 significant digits are provided for the measurement.

Precision for derived parameters as follows:

Parameters	Decimal Places
log 10 of SARS-CoV-2 viral load	2
Time-weighted average change in SARS-CoV-2 viral load	2
BMI	2
CCI	

- 11) Last dose date is not expected to be missing. However, if last dose date is missing, it will be imputed using the maximum of non-missing, non-zero dose, study drug start and stop dates.
- 12) Incomplete death dates will be imputed as the maximum of the study drug start dates, study drug end dates, clinic or phone visit dates (lvis28dt), laboratory visit dates (llab28dt), including the 28-day follow-up visit date plus 1.
- 13) Censoring rules

Time to hospitalization/death: If a participant prematurely discontinues from the study prior to Day 28 or the hospitalization status is missing, the participant is censored at last study date or day 28 whichever is earlier.

Time to negative SARS-CoV-2 viral load, participants are censored at the last assessment day and participants are required to have at least one postbaseline assessment.

Time to alleviation of baseline COVID-19 symptoms:

- For overall baseline symptom alleviation, participants are censored at the last assessment day that at least one of the baseline symptoms was assessed. For baseline symptom alleviation for each domain, participants are censored at the last assessment day that at least one of the baseline symptoms within that domain was assessed

- 14) Graded Laboratory Abnormalities Summary

The following labels will be used for laboratory abnormalities and Grade 3 or 4 laboratory abnormalities summary tables and listings:

Battery	Lab Test Label Used in I-labtox Listing	Toxicity Direction	Lab Test Label Used in t-labtox Table
Hematology	Hemoglobin	Decrease	Hemoglobin (Decreased)
	Lymphocytes	Decrease	Lymphocytes (Decreased)
	Neutrophils	Decrease	Neutrophils (Decreased)
	Platelets	Decrease	Platelets (Decreased)
	WBC	Decrease	WBC (Decreased)
Chemistry	Albumin	Decrease	Albumin (Decreased)
	Alkaline Phosphatase	Increase	Alkaline Phosphatase (Increased)
	ALT	Increase	ALT (Increased)
	AST	Increase	AST (Increased)
	Bicarbonate	Decrease	Bicarbonate (Decreased)
	Corrected Calcium	Increase	Corrected Calcium (Hypercalcemia)
	Corrected Calcium	Decrease	Corrected Calcium (Hypocalcemia)
	Creatine Kinase (CK)	Increase	Creatine Kinase (Increased)
	Creatinine	Increase	Creatinine (Increased)
	Creatinine Clearance	Decrease	Creatinine Clearance (Decreased)
	Lipase	Increase	Lipase (Increased)
	Magnesium	Decrease	Magnesium (Hypomagnesemia)
	Phosphate	Decrease	Phosphate (Hypophosphatemia)
	Serum Glucose (Fasting)	Increase	Serum Glucose (Fasting, Hyperglycemia)
Coagulation	Serum Glucose (Nonfasting)	Increase	Serum Glucose (Nonfasting, Hyperglycemia)
	Serum Glucose	Decrease	Serum Glucose (Hypoglycemia)
	Serum Potassium	Increase	Serum Potassium (Hyperkalemia)
	Serum Potassium	Decrease	Serum Potassium (Hypokalemia)
	Serum Sodium	Increase	Serum Sodium (Hypernatremia)
	Serum Sodium	Decrease	Serum Sodium (Hyponatremia)
	Total Bilirubin	Increase	Total Bilirubin (Hyperbilirubinemia)
	Uric Acid	Increase	Uric Acid (Hyperuricemia)
	Prothrombin Intl. Normalized Ratio (INR)	Increase	Prothrombin Intl. Normalized Ratio (Increased)
	Activated partial thromboplastin time (aPTT)	Increase	Activated partial thromboplastin time (Increased)

15) SAS code for ANCOVA:

```

ods output ParameterEstimates=out1 LSMeans=out2 LSMeanCL=out3
LSMeanDiffCL=out4;
proc glm data=dat1 plots=none;
class trt01pn;
model DAVG = trt01pn base / solution;
lsmeans trt01pn / stderr cl pdiff;
run;

```

```
ods output close; quit;
```

16) Symptom scores in the FLU-PRO questionnaire raw data start from 1 to n (total number of responses in a question), in the FLU-PRO user manual, symptom scores start from 0. In the analysis dataset, symptom scores will be re-mapped to match the scoring in the FLU-PRO user manual for proper calculation of total score and domain score.

17) FLU-PRO Total Score and Domain Score:

The presence and severity of influenza signs and symptoms are assessed across 7 body systems: Nose (4 items), Throat (3 items), Eyes (3 items), Chest/Respiratory (7 items), Gastrointestinal (4 items), Body/Systemic (11 items), and Sense (2 items). For 29 of the items, the severity scale is as follows: 0 (“Not at all”), 1 (“A little bit”), 2 (“Somewhat”), 3 (“Quite a bit”), and 4 (“Very much”). For 5 items, severity is assessed in terms of frequency, i.e., vomiting or diarrhea (0 times, 1 time, 2 times, 3 times, or 4 or more times); with frequency coughed up mucus or phlegm evaluated on a scale from 0 (“Never”) to 4 (“Always”). For 2 items, severity is assessed as 0 (“No”) or 1 (“Yes”).

Domain	Items	Scoring	Minimum Data Requirement
Nose	Runny or dripping nose Congested or stuffy nose Sneezing Sinus pressure	Arithmetic mean of 4 items within Nose domain	Daily score for 3 of 4 items must be present to calculate domain score
Throat	Scratchy or itchy throat Sore or painful throat Difficulty swallowing	Arithmetic mean of 3 items within Throat domain	Daily score for 2 of 3 items must be present to calculate domain score
Eyes	Teary or watery eyes Sore or painful eyes Eyes sensitive to light	Arithmetic mean of 3 items within Eyes domain	Daily score for 2 of 3 items must be present to calculate domain score
Chest/Respiratory	Trouble breathing Chest congestion Chest tightness Dry or hacking cough Wet or loose cough Coughing Coughed up mucus or phlegm	Arithmetic mean of 7 items within Chest/Respiratory domain	Daily score for 5 of 7 items must be present to calculate domain score
Gastrointestinal	Felt nauseous Stomach ache How many times did you vomit? How many times did you have diarrhea?	Arithmetic mean of 4 items within Gastrointestinal domain	Daily score for 3 of 4 items must be present to calculate domain score
Body/Systemic	Headache Head congestion Felt dizzy Lack of appetite Sleeping more than usual	Arithmetic mean of 11 items within Body/Systemic domain	Daily score for 8 of 11 items must be present to calculate domain score

Domain	Items	Scoring	Minimum Data Requirement
	Body aches or pains Weak or tired Chills or shivering Felt cold Felt hot Sweating		
Sense*	Loss Smell Loss Taste	Arithmetic mean of 2 items within Sense domain	Daily score for 1 of 2 items must be present to calculate domain score
Total	All above 34 items	Arithmetic mean of all 34 items within FLU-PRO	In the presence of missing data, the above conditions for the calculation of all domain scores must be met in order to calculate the FLU-PRO total score.

\* Added for COVID-19

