#### **7.3.3. Serious Adverse Events**

All SAEs, regardless of cause or relationship, that occur after the participant first consents to participate in the study (i.e., signing the informed consent) and throughout the duration of the study, including the post-treatment follow-up visit, must be reported on the applicable eCRFs and to GLPS as instructed below in this section. This also includes any SAEs resulting from protocol-associated procedures performed after informed consent is signed.

Any SAEs and deaths that occur after the post-treatment follow-up visit but within 30 days of the last dose of study drug, regardless of causality, should also be reported.

Investigators are not obligated to actively seek SAEs after the protocol-defined follow-up period; however, if the investigator learns of any SAEs that occur after the protocol-defined follow-up period has concluded and the event is deemed relevant to the use of study drug, the investigator should promptly document and report the event to Gilead GLPS.

- All SAEs will be recorded in the case report form (CRF)/eCRF database within 24 hours.

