### **8.5. Efficacy Analysis**

#### **8.5.1. Primary Analysis**

The primary endpoint of the study is the composite endpoint of COVID-19 related hospitalization or all-cause death by Day 28. The null hypothesis being tested is whether the ratio of proportion of COVID-19 related hospitalization or all-cause death is the same for the 2 treatment groups (ie, whether ratio is equal to 1 across all strata).

The hazard ratio, p-value, and 95% CI for the hazard ratio will be calculated using a Cox model with stratification factors as covariates.

Participants with missing outcomes for the primary endpoint due to prematurely discontinuation of the study will be censored at the date of last contact.

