### 3.8. Analysis Visit Windows

#### 3.8.1. Definition of Study Day

Study day will be calculated from the first dosing date of study drug and derived as follows:

- For postdose study days: Assessment Date – First Dosing Date + 1
- For days prior to the first dose: Assessment Date – First Dosing Date

Therefore, study day 1 is the day of first dose of study drug administration.

**Last Dose Date** is defined as the maximum, nonmissing, nonzero dose end date of treatment recorded on the Study Drug Administration eCRF form with “Study Drug Permanently Withdrawn” box checked for participants who prematurely discontinued or completed study drug according to the Study Drug Completion eCRF. Refer to [Appendix 2](#) for missing date imputation, if necessary.

**Last Study Date** is the latest of the study drug start dates and end dates, the in-person or phone visit dates, the vital sign or respiratory status collection dates, Flu-PRO Plus questionnaire collection date and the laboratory collection dates, including the 28-day follow-up visit date, and the death date (if applicable, only for participants who prematurely discontinued study according to the Study Completion eCRF).

**Baseline value** is defined as the last value obtained on or prior to the first dose date (and time, if available) unless otherwise specified (see Section [3.8.3](#)).

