## 6. EFFICACY ANALYSES

### 6.1. Primary Efficacy Endpoint

#### 6.1.1. Definition of the Primary Efficacy Endpoint

The primary endpoint of the study is the composite endpoint of COVID-19 related hospitalization (defined as at least 24 hours of acute care) or all-cause death by Day 28. The endpoint will be derived by combining the available all-cause death and COVID-19 related hospitalization reported by the site. The first COVID-19 related hospitalization will be used for the proportion of COVID-19 related hospitalization or all-cause death.

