#### 6.1.3. Primary Analysis of the Primary Efficacy Endpoint

The hazard ratio of COVID-19 related hospitalization or all-cause death between the two treatment groups will be estimated using a Cox model with stratification factors as covariates.

If a participant prematurely discontinues from the study prior to Day 28 or the hospitalization status is missing, the participant is censored at last study date or day 28 whichever is earlier. If a participant has a COVID-19 related hospitalization first and then dies, then date of the COVID-19 related hospitalization and status will be used for the primary analysis for this participant. If a participant has a non COVID-19 related hospitalization first and then dies without experiencing a COVID-19 related hospitalization, then date of the death and status will be used for the primary analysis for this participant.

The hazard ratio, p-value, 95% CI for the hazard ratio from Cox model, and proportion of COVID-19 related hospitalization or all-cause death at Day 28 from Kaplan-Meier estimate will be provided.

The FAS will be the primary analysis set for efficacy endpoint evaluation. The primary endpoint may be analyzed for each of the subgroups defined in Section 3.3.

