#### **7.1.6.2.      Incomplete Dates**

If the onset date of the AE is incomplete and the AE stop date is not prior to the first dosing date of study drug, then the month and year (or year alone if month is not recorded) of onset determine whether an AE is treatment emergent. The event is considered treatment emergent if both of the following 2 criteria are met:

- The AE onset date is the same as or after the month and year (or year) of the first dosing date of study drug, and
- The AE onset date is the same as or before the month and year (or year) of the date corresponding to 30 days after the date of the last dose of study drug

An AE with completely missing onset and stop dates, or with the onset date missing and a stop date later than the first dosing date of study drug, or with the onset date missing and the AE is marked as ongoing, will be considered to be treatment emergent. In addition, an AE with the onset date missing and incomplete stop date with the same or later month and year (or year alone if month is not recorded) as the first dosing date of study drug will be considered treatment emergent.

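### The rule for incomplete death dates ignores a recorded month or year and omits some contact dates, so in rare cases a death after Day 28 could be dated within Day 28

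*SAP*

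**What the plan says.** SAP Appendix 2 item 12 gives one rule for every incomplete death date: "Incomplete death dates will be imputed as the maximum of the study drug start dates, study drug end dates", followed by clinic or phone visit dates and "laboratory visit dates (llab28dt), including the 28-day follow-up visit date plus 1". It has no branch for a known month or year and does not separate partial dates from wholly missing ones.

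Four other places decide what the imputed date does:

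- **Primary endpoint (SAP 6.1.1).** "The endpoint will be derived by combining the available all-cause death and COVID-19 related hospitalization reported by the site".
- **Censoring (SAP 6.1.3, repeated in Appendix 2 item 13).** For anyone who discontinues before Day 28, or whose hospitalization status is missing, "the participant is censored at last study date or day 28 whichever is earlier". Protocol 8.5.1 is narrower: "Participants with missing outcomes for the primary endpoint due to prematurely discontinuation of the study will be censored at the date of last contact".
- **Last Study Date (SAP 3.8.1).** It takes the latest of dosing, visit, vital-sign, respiratory-status, FLU-PRO Plus and laboratory dates, "and the death date (if applicable, only for participants who prematurely discontinued study according to the Study Completion eCRF").
- **Reporting of late deaths (Protocol 7.3.3).** "Any SAEs and deaths that occur after the post-treatment follow-up visit but within 30 days of the last dose of study drug" are also to be reported.

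**The concern.** Death counts in the primary composite, in the Day 14 composite, in the medically attended visit composites and as a secondary endpoint of its own. A rule that discards a recorded month can contradict data on file: the month may prove that the death came after Day 28 while the imputed date says it did not. That would add a primary event which did not occur within the window.

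The list of dates in item 12 is also shorter than the list in Last Study Date, and it has no hospitalization dates. An imputed death can then fall before a day on which the participant was demonstrably alive. It can also fall before a COVID-19 hospitalization that SAP 6.1.3 says should supply the event date.

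**Working it through.** **1. Where item 12 puts the death.** Let d be the study day of the last date on item 12's list. The plain reading gives Day d + 1. If the words about adding 1 belong only to the 28-day visit, a discontinuer without that visit gets Day d. Both are by Day 28 for every d up to 27, whatever month is recorded.

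**2. Early discontinuer (assumed dates).** First dose 1 February 2021 = Day 1; last listed contact 14 February = Day 14; death recorded only as March 2021.

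- Item 12: 15 February = Day 15.
- Earliest possible date: 28 February is Day 28, so 1 March is Day 29.
- Reporting window: last dose Day 3 + 30 = Day 33 = 5 March. A death on 1 to 5 March is one that Protocol 7.3.3 requires to be reported.

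Whether Day 15 becomes an event depends on which text governs. SAP 6.1.3 and item 13, read literally, censor anyone who discontinues before Day 28. Protocol 8.5.1 censors only missing outcomes, and a known death is not one. SAP 3.8.1 places the death date inside Last Study Date for these same participants. The second reading is the more natural, but the SAP does not state it.

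**3. Completer.** The Day 28 visit window is ±5 days (Protocol 6.5), so the visit can fall on Days 23 to 33. Visits on Days 23 to 27 give an imputed death on Days 24 to 28; visits on Day 28 or later give Day 29 or later. With first dose 1 February, a visit on 25 February (Day 25) and a death recorded as March 2021, item 12 gives 26 February = Day 26, a primary event. The early-discontinuation clause does not apply to a completer.

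**4. How narrow the condition is.** For a death on Days 29 to 33 to be shown late by its month alone, the first of a month must fall on Days 29 to 33. That is about 5 of every 30 start dates.

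**5. Omitted dates.** Suppose the last date on item 12's list is Day 7, a FLU-PRO Plus diary is completed on Day 9 and a COVID-19 admission occurs on Day 10. An incomplete death date becomes 7 + 1 = Day 8, before both. Here the event count is unchanged but the event time is wrong.

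**6. Size of one misplaced event.** Inputs: 584 randomized (SAP 2.1.1), assumed split 292 per arm; planned rates 12% and 6.6% (SAP 1.3). The approximation is HR = ln(1 − a/292) / ln(1 − b/292), with a = remdesivir and b = placebo events, and SE of ln HR = √(1/a + 1/b). The same form reproduces the planned hazard ratio: ln(0.934)/ln(0.88) = 0.534. Expected events: 292 × 0.066 ≈ 19 and 292 × 0.12 ≈ 35.

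| Events, remdesivir vs placebo | HR | p |
|---|---|---|
| 19 vs 35 | 0.527 | 0.025 |
| 20 vs 35 (one more remdesivir) | 0.556 | 0.036 |
| 19 vs 36 (one more placebo) | 0.511 | 0.018 |

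At half the planned rates (10 vs 18) HR 0.548 becomes 0.604 or 0.518. At a quarter (5 vs 9) HR 0.552 becomes 0.663 or 0.496.

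**The case against.** The strongest reply is that this rule will hardly ever be used. Deaths are serious adverse events sent to the sponsor within 24 hours (Protocol 7.3.3.1), reconciled with the safety database (SAP 7.1.5) and queried before the final analysis (SAP 2.2). Nothing in the documents shows that a single partial death date exists, or that such dates come mainly from dropouts. That stands, and it limits the priority of the point.

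Four stronger readings are tempting, and the documents do not support them:

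- **That a late death after withdrawal simply becomes a primary event.** The literal censoring sentence in SAP 6.1.3 points the other way, so for discontinuers the result is conditional.
- **That the Day 28 mortality comparison is at similar risk.** SAP 6.2.1 removes participants who discontinue before Day 28 from the Fisher test, so the exposure there is mainly through completers.
- **That the rule threatens significance.** Two extra events placed only in the remdesivir arm (21 vs 35) would give p = 0.052 by the same approximation. But the rule is identical in both arms, and no text supports even one case.
- **That the SAP breaks its own convention.** In SAP 7.1.6.2, "then the month and year (or year alone if month is not recorded) of onset determine whether an AE is treatment emergent". That rule classifies a record as inside or outside a window, whereas item 12 must supply a single date for a time-to-event model. The contrast shows that month and year logic is available to the programmers; it is not a contradiction.

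An example with a death around Day 41 or later would also be weak, because Protocol 7.3.3 does not require such deaths to be sought. The example with first dose on 1 February avoids this.

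**Conclusion.** The point holds as a minor defect in a stated rule for a primary-endpoint component. As written, item 12 can date a death by Day 28 when the recorded month excludes it, and can date a death before the participant was last known alive. No other section corrects either fault.

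The first fault produces a false primary event for completers seen on Days 23 to 27. For early discontinuers it does so only if a recorded death overrides censoring. The number of cases is unknown and probably very small, and the direction of any error is open. The p-values rest on an assumed equal split, planned event rates and a Wald approximation. They show the leverage of one event and do not forecast a result.

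**What to change.** Reword SAP Appendix 2 item 12 as follows:

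1. For a partial death date, impute the later of (a) the last date known alive plus 1, using every date in Last Study Date other than the death date, together with hospitalization dates, and (b) the first day of the recorded month, or of the recorded year if only that is known. Query any case where the result conflicts with the recorded month.
2. For a completely missing death date, keep the last date known alive plus 1, from the same fuller list.
3. Add to SAP 6.1.3 and item 13 that a recorded death on or before Day 28 is an event and is not censored.
4. If the recorded month spans Day 28, report the primary result with that death counted and not counted.

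In the example with first dose on 1 February, this gives 1 March = Day 29 and no event by Day 28.

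The change needs no new data. Its cost is one small sensitivity analysis, run only if such a case exists. The first of the month is still an earliest-possible date, so some early dating remains; step 4 covers the cases where that affects the event count. The change should be made before unblinding, so that it is not chosen in knowledge of the arm it favours.
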